DNase RCT in adults: A pivotal randomized controlled trial led by Rahman et al. from the UKCRC Oxford Respiratory Trials Unit was recently published in the New England Journal of Medicine addressing the effectiveness of DNase in adult patients.⁴² The authors conducted a blinded 2-by-2 factorial trial in which 210 adult patients with pleural infections were randomly assigned to four study treatments for 3 days: double placebo, intrapleural tPA and DNase, tPA and placebo, or DNase and placebo. The primary outcome was the change in pleural opacity, measured as the percentage of the hemithorax occupied by effusion on chest radiography on day 7 compared with day 1. Secondary outcomes included referral for surgery, duration of hospital stay and adverse events. For the primary outcome, the authors found a significantly greater reduction in pleural opacity in the tPA-DNase group compared with the placebo group ($-29.5 \pm 23.3\%$ vs. $-17.2 \pm 19.6\%$; mean difference -7.9% ; 95% confidence interval (CI), -13.4 to -2.4 ; $p=.005$). The change in pleural opacity observed with tPA alone or DNase alone was not statistically different from that observed with placebo. All secondary outcomes also pointed to superiority of tPA-DNase compared with other study arms. Hospital stay for the tPA-DNase group (11.8 ± 9.4 days) was about 50% shorter compared with placebo (24.8 ± 56.1 days), whereas in the DNase-only group and the tPA-only group, length of stay was similar to placebo. The frequency of surgical referral at 3 months was lower in the tPA-DNase group compared with placebo (4% vs. 16%; odds ratio for surgical referral, 0.17; 95% CI, 0.03 to 0.87, $p=.03$). Surgical referrals were increased in the DNase-only group (odds ratio, 3.56; 95% CI, 1.30-9.75, $p=.01$), and were non-significantly reduced in the tPA-only group (odds ratio, 0.29; 95% CI, 0.07 to 1.29, $p=.1$). Mortality rates were 8% at 3 months and 12% at 12 months, but were similar across all study groups. Inflammatory measures (C-reactive protein, systemic white blood cell count and odds of fever) were also assessed. Significant ($p<.05$) differences were found in mean white count on day 7 and fever on day 6 or 7 between tPA-DNase and placebo. The new treatment was not associated with any excess of adverse events. Serious adverse events described included intrapleural hemorrhage ($n=2$, both in the tPA-DNase group), gastrointestinal bleeding ($n=2$, both in the DNase group), hemoptysis ($n=1$, in the tPA-DNase group), and clinical deterioration ($n=1$, in the placebo group).

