- a. *Time to meeting discharge criteria:* This is defined as the time, measured in hours, and reported in days rounded to a single decimal point, from insertion of the chest drain to meeting discharge criteria. This will be assessed by a research assistant on a twice daily basis (9 AM and 4 PM) and defined as: no fever (temperature less than 38°C) for 24 hours, normal respiratory rate for age [using the World Health Organization (WHO) age-specific criteria (< 50 breaths/min for 2-12 months, < 40 breaths/min

for 1 to 5 years, and < 20 breaths/min for ≥ 5 years)], no hypoxia (transcutaneous oxygen saturations in room air less than 92%), and drinking fluids well.

b. *Time to drain removal*: This is defined as the time, measured in hours, and reported in days rounded to a single decimal point, from drain insertion to drain removal.

c. *Duration of fever after intervention*: This is defined as the duration, measured in hours, and reported in days rounded to a single decimal point, of fever (defined as temperature $>38^{\circ}\text{C}$ taken by any method) from insertion of the chest drain until resolution. This will be recorded by a research assistant daily.

d. *Need for ventilatory support or non-invasive ventilation following the intervention*.

e. *Serious bleeding*: This is defined as intrapleural bleeding resulting in a drop in hemoglobin of greater than 20 g/L or needing a transfusion.

f. *Need for further interventions*: This is defined as the need for further intervention such as placement of another chest drain (by any technique) or surgical intervention such as thoracotomy and decortication, video-assisted thoroscopic surgery, or pneumonectomy.

g. *Hospital readmission*: Any hospital readmission after discharge from hospital for initial treatment for pleural empyema within three months related to pleural empyema or its treatment (e.g. harm). All hospital readmissions will be categorized as empyema-related or not.

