h. *Cost of the hospitalization*: An economic evaluation will compare the relative costs of DNase-tPA with tPA alone in previously well children who present with pleural empyema, using patient-level data from the trial. We will conduct the analysis from a hospital's perspective because hospital administrators will be making reimbursement decisions for this intervention. Since empyema is an acute condition and the long-term consequences are negligible, the time horizon of the analysis will be the length of hospital stay. Since the primary effectiveness outcome is length of hospital stay or time to hospital discharge, which can be expressed in monetary terms (i.e. hospitalization cost), we will only compare the costs of the two strategies to avoid double-counting the effectiveness. The cost of each patient includes the cost of intervention (DNase-tPA or tPA alone) and costs incurred during the hospital stay ("hospitalization cost"). We will obtain the hospitalization costs of each patient from case costing data from hospital financial departments. We will calculate mean cost per patient by intervention group, based on initial intervention assignment, and incremental cost using simple linear regression:

$$C_i = \alpha_i + \beta t_i + \varepsilon_i$$

Where C_i is the cost for each patient i , α is the intercept term, t is an intervention dummy term ($t=1$ if the patient received DNase-tPA and $t=0$ for tPA alone), and ε is the stochastic error term. The regression coefficient β estimates the incremental cost of DNase-tPA compared with tPA alone. The regression statistics will show mean cost per patient by intervention group and the uncertainty around the mean estimates. We will also conduct sensitivity analysis to assess the robustness of the results.

i. *Mortality*: this will include mortality from any cause during the hospitalization for empyema.

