Blinding: Patients, their parents or other caregivers, site investigators, research assistants and coordinators, treating physicians (pediatricians, radiologists, and interventional radiologists or surgeons), treating nurses, and data managers will be blinded to the treatment allocation. Group allocation will be concealed until the final data analysis is performed. Intervention drugs will be blinded by the research pharmacy. Both arms will be constituted by the research pharmacies in clear liquids in a polyethylene container⁴² in a manner such that both are identical (packaging, colour, volume, texture, and odour) to ensure blinding. After obtaining the treatment number from the central randomization centre, the study pharmacist will retrieve the corresponding vial and one of its treatment number labels will be attached to the patient's case report form (CRF).

Unblinding Procedures: We do not anticipate any circumstances that would require unblinding as knowledge of study arm is not anticipated to affect any treatments for patients.

Data collection methods: Data collection for outcome measures will be mainly collected in hospital by the Research Assistant (RA). At baseline, the following data will be obtained: age, sex, duration of antibiotic treatment prior to chest drainage insertion (days), duration of fever prior to chest drain insertion (days), hypoxia in room air (oxygen saturations less than 92% in room air prior to intervention), microbiologic identification of causative agent (blood culture results, throat swab, pleural fluid culture, pleural fluid PCR), ultrasound of chest: pleural effusion size >10 mm <10 mm, stage of empyema on ultrasound of chest: Stage 1: anechoic nonseptated fluid; Stage 2: echoic fluid without septation; and Stage 3: septated fluid and Stage 4: septations with solid appearing components comprising more than one third of the effusion.⁵³ All ultrasounds will be reviewed by a blinded study radiologist (BC). In addition, patients will receive a follow-up phone call from the RA at 3 months enquiring about any possible readmissions and ongoing symptoms of fever, shortness of breath and/or exercise intolerance.

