Primary outcome: Data will be analyzed according to intention to treat principles for the primary outcome (e.g. patients who do not receive all three doses of study drug will be analyzed in the group they were assigned to). Exceptions to this principle will only include any patient who dies in hospital and will be excluded from the analysis of time to hospital discharge. Given that the primary outcome and other acute secondary outcomes are obtained during hospitalization, it is anticipated that there will be no missing data for these outcomes with the possible, but unlikely exception of in-hospital death, which is rare in childhood empyema. For the follow up outcomes at 3 months, the proportion of patients who follow up will be presented for each treatment arm, and patients who are lost to follow up will be stated but omitted from the analysis. The primary outcome, time (in days) to hospital discharge, will be described as the difference between the two means with the 95% confidence intervals. The student's t-test (independent two sample test assuming equal group size and variance), will be used to detect a difference between the two treatment groups. If the resulting data is inappropriate for a t-test (increasing variance with the mean is the biggest concern since the test is quite robust to non-normality in the population), a suitable transformation or non-parametric test may be used. If feasible, a secondary analysis of the primary outcome will analyze time to discharge, treating death as a competing risk, using methods for survival data. Since randomization is stratified between five centres, the analysis will adjust for this stratification by including centre as a covariate in a multiple linear regression model, to obtain adjusted treatment effects. Additionally, a treatment by centre interaction will be tested to see if the treatment effect differs between centres. Subgroup analyses will also be conducted to explore any potential differences in outcomes by age or sex.

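### Mortality is limited to the index stay, and serious bleeding and further interventions have no stated window; read as in-hospital counts, all three are observed over a stay the treatment is meant to shorten

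*Combined protocol and SAP*

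**What the plan says.** All references are to the combined protocol and SAP.

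- **Mortality** (Outcomes - Secondary outcomes, i): "this will include mortality from any cause during the hospitalization for empyema". The window closes at index discharge.
- **Serious bleeding** (item e): "This is defined as intrapleural bleeding resulting in a drop in hemoglobin of greater than 20 g/L or needing a transfusion". No start or end is given.
- **Need for further interventions** (item f): "This is defined as the need for further intervention such as placement of another chest drain (by any technique) or surgical intervention", followed by examples. Again no start or end is given.
- **Where the data come from** (Statistical Analysis, Primary outcome): "Given that the primary outcome and other acute secondary outcomes are obtained during hospitalization", no missing data are expected. The next sentence deals separately with follow-up outcomes at 3 months.
- **After discharge** (Data collection methods): "patients will receive a follow-up phone call from the RA at 3 months enquiring about any possible readmissions", and about ongoing symptoms. Deaths, chest procedures and bleeds are not listed.
- **Readmission** (item g): counted for three months after discharge if related to the empyema or its treatment, with harm given as an example.
- **Analysis** (Secondary outcomes and exploratory outcome): dichotomous outcomes are compared as proportions with Fisher's exact test and a relative risk. The list names serious bleeding, further interventions, ventilatory support and mortality. It does not name readmission.
- **Hypothesis** (Secondary Hypotheses, b): DNase-tPA will not increase any of these events.

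**The concern.** If items e and f are counted only in hospital, as item i expressly is, the counting period for each child is the time from drain insertion to discharge. That is the primary outcome. A treatment that works as hypothesised shortens the period over which its own failures and harms are counted, and simple proportions make no allowance for this.

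Take a child who goes home early and returns for a second drain or an operation. On the in-hospital reading this child has a short primary outcome and no further intervention under item f. The return appears only under item g, which records that the child came back but not that a procedure was needed. The same procedure done before discharge would have counted under f.

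What is at stake is how hypothesis (b) can be read. A trial whose endpoint is discharge time should be able to show directly whether earlier discharge was followed by later procedures. The adult trial that the plan builds on reported a comparable event over a fixed horizon: "The frequency of surgical referral at 3 months was lower in the tPA-DNase group compared with placebo".

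**Working it through.** **1. The plan's own sample size.** Inputs from Sample size: difference 2 days, SD 2.9, two-sided alpha 0.05, power 90%.
- Normal approximation: n = 2 x (1.96 + 1.2816)^2 x 2.9^2 / 2^2 = 44.2, so 45 per group.
- Two-sample t test: 45.17, so 46 per group, with power 90.5% at 46. This matches the stated 46.
- With 5% inflation: 46 x 1.05 = 48.3, so 49 per group, as stated. Nothing below changes this number.

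**2. In-hospital observation if the target effect is real.** The control mean is 6.8 days (Sample size).
- DNase-tPA mean: 6.8 - 2 = 4.8 days.
- Patient-days: 49 x 6.8 = 333 against 49 x 4.8 = 235. The ratio is 0.71, or 29% less.
- Over the published control range of 6 to 15 days, the ratio runs from 4/6 = 0.67 to 13/15 = 0.87, or 33% to 13% less.

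**3. Expected events per arm.**
- Further procedures, 17% to 38% (Deoxyribonuclease section): 49 x 0.17 = 8.3 to 49 x 0.38 = 18.6.
- Clinically significant bleeding, 2% (Fibrinolytics): 49 x 0.02 = 0.98.
- Deaths: the section on extrapolating from the adult trial reports none in paediatric empyema RCTs.

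**4. Upper-end illustration.** Assume no true effect on events, a constant daily rate over the stay, and every child staying the mean time. If p is the control proportion, the proportion seen in the DNase-tPA arm is q = 1 - (1 - p)^(4.8/6.8).

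| Outcome | p | q | Apparent RR | Expected events, tPA v DNase-tPA |
|---|---|---|---|---|
| Serious bleeding | 2% | 1.4% | 0.71 | 0.98 v 0.69 |
| Further procedures, low | 17% | 12.3% | 0.72 | 8.3 v 6.0 |
| Further procedures, high | 38% | 28.6% | 0.75 | 18.6 v 14.0 |

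Under the same assumptions, a true daily rate 6.8/4.8 = 1.42 times higher with DNase-tPA would show as equal proportions.

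**5. Lower end.** Dosing ends at about 48 hours in both arms, inside even a 4.8-day mean stay. If events cluster in the dosing period, almost none fall after discharge and the artefact is near zero.

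**6. A middle case.** The documents do not give the share of procedures that arise after discharge. Assuming 5% to 15%, the missed events run from 0.05 x 8.3 = 0.4 to 0.15 x 18.6 = 2.8 per arm, split unequally if stays differ.

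**7. Readmission for comparison.** Take three months as 91 days. Total follow-up from drain insertion is 4.8 + 91 = 95.8 days against 6.8 + 91 = 97.8 days, a ratio of 0.98. Outcome g is almost free of the problem.

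**The case against.** The strongest reply is that the plan never says items e and f stop at discharge. Item f covers "placement of another chest drain (by any technique) or surgical intervention such as thoracotomy and decortication" with no cut-off and no exclusion of readmissions. The remark that acute secondary outcomes are obtained in hospital does not list those outcomes and sits in a passage about missing data. This stands in part: for e and f the in-hospital window is an inference. It is a fair one, because the same passage sets acute outcomes apart from 3-month outcomes and the 3-month call lists neither procedures nor bleeds. Even on the generous reading, five centres have no rule for classifying a drain placed at readmission.

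Three stronger readings are tempting, and the documents do not support them.

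- *Late events are lost in the DNase-tPA arm only.* Children in both arms go home, so both can lose late events. The most that can be said is that the loss may be greater in the arm with shorter stays. A further procedure also lengthens the stay, so this is not simple truncation.
- *The trial cannot detect earlier discharge bought with later procedures.* A second drain or operation after discharge would nearly always need a readmission. Item g counts related readmissions over an equal post-discharge period in both arms, and readmission is named in hypothesis (b). The Data Monitoring Committee also receives deaths, surgical events and adverse events with no discharge limit stated.
- *Harms in general are followed only to discharge.* Treatment-related readmission, expressly including harm, is followed for three months.

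Two further points stand. The adult measure was surgical referral, not surgery, and the plan explains why paediatric disease differs. The plan also declares its secondary analyses hypothesis generating.

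**Conclusion.** The point holds as a cheap improvement. Mortality is limited to the index stay by explicit wording. Further interventions and serious bleeding have no stated window, and the most natural reading of the analysis section gives them the same one. On that reading the counting period is the primary outcome, 29% shorter with DNase-tPA if the target effect is met (13% to 33% over the published range of stays).

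The practical size is probably small. For mortality it is near zero. For bleeding about one event per arm is expected, so no window would make that comparison informative. For further interventions it ranges from near zero, if events cluster in the dosing period, to an apparent relative risk of 0.72 to 0.75 under a constant daily rate, which is an upper-end assumption. The unknown is the share of procedures that arise after discharge, and the documents give no figure for it. All these sizes also depend on DNase-tPA actually shortening the stay. Outcome g limits the damage, but it does not record the procedure and is not in the list of dichotomous outcomes to be tested.

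**What to change.** 1. Define further intervention, serious bleeding and death over one fixed period from drain insertion with a common end day, for example 90 days. The call is made three months after discharge (Ethical Considerations), so day 90 from drain insertion falls before every child's call. The date of the call itself should not be the end point, because it moves with discharge.
2. State that a drain, operation or serious bleed at a readmission within that period counts under item e or f, as well as under g.
3. Add death and any chest procedure to the 3-month call.
4. Keep the in-hospital counts as a supporting table.

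The sample size, Fisher's exact test and the relative risk stay as planned, and no visit is added. The cost is outcome wording and two items on a call already planned. The downside is that post-discharge events rest on parent report and readmission records, and on children reached at 3 months. The plan omits those lost to follow-up. In the team's earlier cohort of 88, 6 (7%) were lost at one month and a further 8 (9%) at six months, so some incompleteness should be expected and reported by arm.

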Recruitment: All study patients will be initially identified by research assistants who will review both (a) all new admissions to the relevant inpatient units in each study centre twice daily; and, (b) all referrals for chest drainage insertion at each centre. It is anticipated that most drains at both sites will be inserted by interventional radiologists, although a minority may be inserted by general surgeons. Physicians and radiologists/surgeons will also be asked to notify the site research assistant and/or site investigator of children admitted with pleural empyema who may be eligible for the study. Patients will be approached, eligibility criteria confirmed, consent obtained, and enrolled after the decision to refer for chest drainage but before chest drain insertion occurs.

Randomization – Sequence generation, allocation concealment and implementation: After informed consent is obtained, patients will be randomized into treatment groups using a random allocation sequence facilitated by the Applied Health Research Centre (AHRC), which will be the coordination and management centre for the trial and administered by the hospital research pharmacies. Randomization will be stratified by centre. Blocking will be used to ensure that the two comparison groups are about the same size throughout the trial for each center and for the trial as a whole (about 49 per group). An allocation ratio of 1:1 with random block size will be used within each stratum (centre). This will help to ensure that clinicians, investigators, or outcome assessors will not decipher the block size. A computer-based pseudo-random number generator will be used to create treatment allocation tables for each study center. After patient eligibility has been confirmed and consent obtained and just as the patient leaves the inpatient unit to the radiology suite or operating room for chest drain insertion, the site investigator, or his/her delegate, will assign the patient a unique study identification (ID)

number in sequential order. The study ID will correspond with the randomization table held in the research pharmacy for dispensing blinded DNase or placebo. The biostatistician will maintain a secure master list of the randomization codes and the assigned treatments will be checked against the master list at the end of the study.

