Secondary outcomes and exploratory outcome: For the secondary and exploratory outcomes that are continuous variables (e.g. duration of drain insertion, hospital stay after intervention to meeting discharge criteria, duration of fever after the intervention, amount of hemithorax occupied by pleural effusion in radiographs) the difference between the two means with the 95% confidence intervals will be presented. The student's t test will be used to detect a difference between the treatment groups. Dichotomous outcomes (serious bleeding, need for further interventions, need for ventilatory support, mortality) will be described as the absolute number and proportion. A Fisher's exact test will be used to detect a significant ($p < 0.05$) difference between the two treatment arms. The treatment effect will also be presented as the relative risk with 95% confidence intervals. These analyses will be viewed as hypothesis generating, and therefore, no correction for multiple testing is planned.

Data Monitoring and Safety: Data monitoring will be conducted with a Data Monitoring Committee (DMC) composed of a pediatric hospitalist, a respiratory physician and an interventional radiologist. The DMC will be completely independent of the investigators, and will be provided with clinical information from the trial case report forms for death, surgical events and adverse events, including those that were described in the adult DNase trial (hemoptysis, gastrointestinal bleeding, chest pain, nausea, transient confusion and rash). The DMC will be able to request additional information from clinicians.

Adverse Event Reporting: All serious unexpected adverse events will be reported to the REB; as per SickKids REB guidelines. All serious adverse drug reactions to the study medication will be reported to Health Canada within 15 calendar days or for death or life-threatening events, within 7 calendar days. In the latter case, a follow-up report will be filed within 8 calendar days. Adverse reactions will be managed according to the standard clinical management practices. All adverse events and adverse reactions will also be reported to the PI within 24 hours.

[figure not shown]
Quality Assurance: This project will be monitored by The Applied Health Research Centre (AHRC) during the data collection phase of the project. The aim is to ensure that all researchers are maintaining

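### As written, the plan gives the data monitoring committee no means of comparing harms between the two arms

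*Combined protocol and SAP*

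**What the plan says.** Four parts of the combined protocol and SAP bear on this.

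- **Blinding.** The list of blinded parties covers families, site and research staff and treating physicians, and ends "treating nurses, and data managers will be blinded to the treatment allocation". The next sentence is general: "Group allocation will be concealed until the final data analysis is performed". Unblinding Procedures then says that no circumstance requiring unblinding is expected.
- **Randomization.** "The biostatistician will maintain a secure master list of the randomization codes". Its one stated purpose is to verify, once the trial is over, which treatment each child was given. The research pharmacies hold a table for dispensing. No other use of the codes is described.
- **Data Monitoring and Safety.** The committee is independent of the investigators and is "composed of a pediatric hospitalist, a respiratory physician and an interventional radiologist". It "will be provided with clinical information from the trial case report forms for death, surgical events and adverse events". Also: "The DMC will be able to request additional information from clinicians".
- **DNase RCT in adults.** Two intrapleural hemorrhages were reported as serious adverse events, "both in the tPA-DNase group". The same section says that the new treatment brought no excess of adverse events.

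The documents do not mention by-arm or coded-arm safety tables, a statistician to prepare them, or times at which the committee reviews data.

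**The concern.** Children in both arms have a drain inserted and receive tPA. The Fibrinolytics section says that it is hard to tell whether a clinically significant bleed came from the insertion or from the drug. Reviewing a single case therefore cannot attribute a bleed to DNase; that takes a comparison of the arms. Serious bleeding is a listed secondary outcome, with a stated hypothesis that DNase does not increase it, and the protocol says that data for children are lacking.

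Every source that the plan opens to the committee lacks the arm. The case report form carries only a treatment number, and the clinicians are blinded. If harm accumulated in the DNase arm, the committee could become uneasy about the overall rate, but the plan gives it no described way to learn whether the added drug was involved before the trial ended.

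**Working it through.** **Inputs.** From the documents: 49 per arm, 98 in total (Sample size), and a 2% background rate of clinically significant bleeding from drain insertion and/or fibrinolytic (Fibrinolytics). That rate is defined by a drop in hemoglobin. The trial's serious-bleeding outcome needs a drop of more than 20 g/L or a transfusion, so 2% is only an approximate control-arm rate. All DNase-arm rates below are assumptions.

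**The plan's own figure.** For a 2-day difference, SD 2.9, two-sided alpha 0.05 and 90% power, the two-sample t-test needs 45.17, so 46 per group. Then 46 × 1.05 = 48.3, so 49. The plan's numbers reproduce, and nothing here changes them.

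**What a pooled count can show.** With X ~ Binomial(98, 0.02), P(X ≥ 5) = 0.047 and P(X ≥ 6) = 0.014. Six bleeds in 98 (6.1%) would stand out against 2%.

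**What it cannot show.** The same six bleeds fit quite different splits (Fisher's exact test, 49 per arm):

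- 3 v 3: p = 1.00
- 4 v 2: p = 0.68
- 5 v 1: p = 0.20
- 6 v 0: p = 2 × C(49,6)/C(98,6) = 2 × 13,983,816/1,052,618,392 = 0.027

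The pooled report is identical in all four.

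**Range of assumed DNase-arm rates, control arm at 2%.** Expected bleeds are 49 × (0.02 + p). The probabilities come from exact enumeration of two binomial arms.

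| DNase-arm rate | Expected bleeds in 98 | P(pooled ≥ 5) | P(at least 3 more bleeds on DNase) | P(Fisher p < 0.05 against DNase) |
|---|---|---|---|---|
| 4% | 2.9 | 0.172 | 0.174 | 0.005 |
| 6% | 3.9 | 0.355 | 0.373 | 0.030 |
| 8% | 4.9 | 0.547 | 0.568 | 0.088 |
| 10% | 5.9 | 0.710 | 0.725 | 0.182 |
| 15% | 8.3 | 0.932 | 0.932 | 0.495 |

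**Why the arm label matters.** Compare 8% v 2% with 5% v 5%, which have the same average. Their pooled-count distributions are almost the same (total variation distance 0.005), so five or more pooled bleeds has a probability of about 0.55 under either. By arm, an excess of at least 3 bleeds on DNase has probability 0.568 under 8% v 2%, 0.119 under 5% v 5% and 0.035 under 2% v 2%.

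**What a typical split looks like.** At 2% v 10% the expected counts are 49 × 0.02 = 0.98 and 49 × 0.10 = 4.9, about 1 v 5, for which Fisher p = 0.20. A 6 v 0 split against DNase has probability C(49,6) × 0.10^6 × 0.90^43 × 0.98^49 ≈ 0.056 under those rates, so it shows the ambiguity of a pooled count and is not a forecast.

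**The case against.** The committee is not on the list of blinded parties, and the concealment sentence follows that list, so it could be meant for those roles only. The plan does not say that the case information is pooled. The treatment number on each form could be linked to the arm through the biostatistician's list. A charter outside these documents might set this out. All of this is fair. A reader might infer that the committee is formally blinded or barred from the codes; no sentence says so. What stands is that the concealment sentence carries no exception, no route to the codes is described, and no charter is mentioned. A charter that provided by-arm reports would conflict with that sentence as worded.

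A pooled count is not useless, either. At 2% v 10% it reaches five or more about 71% of the time, whereas a by-arm Fisher test reaches p < 0.05 against DNase only about 18% of the time. That disposes of any suggestion that an excess would pass as an unremarkable overall rate. It does not answer which arm carries the excess, and the clinicians to whom the committee may turn do not know the arm.

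Other protections exist. Study drug is discontinued in any child with serious bleeding or anaphylaxis, and Adverse Event Reporting sets deadlines to the lead investigator and the regulator. These act on single cases and do not compare groups. The adult signal is only two events, set beside a statement of no excess overall: a reason to look by arm, not evidence of harm.

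**Conclusion.** The point holds in this form: followed as written, the plan makes no provision for the committee to compare harms by arm while the trial is running. A reader might go further and conclude that safety monitoring cannot work at all. The documents do not support that, since the committee sees individual deaths, surgical events and adverse events and can notice a high overall rate.

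The loss is attribution. Six bleeds in 98 could be an even split or all in one arm, and the committee would have no described way to tell. By-arm counts would not give a decisive test at 49 per arm: the chance of Fisher p < 0.05 against DNase runs from 0.005 to 0.495 over assumed DNase-arm rates of 4% to 15%. They would inform judgement. The calculations rest on the cited 2% as an approximate control rate and on assumed DNase-arm rates. The textual conclusion depends on neither. The plan should be changed, because this is a stated rule that weakens safety oversight in a pediatric trial and it is easily mended.

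**What to change.** 1. **Blinding.** Limit the concealment sentence to everyone outside the DMC reporting process.
2. **Data Monitoring and Safety.** Add that the biostatistician who holds the codes sends the DMC, in closed session, tables of deaths, bleeding, surgical events and adverse events by coded arm (A/B, decodable at the DMC's request) at set enrolment points. State that the tables contain no efficacy comparison.
3. **Firewall.** State that these tables go to the DMC only, so that investigators and sites stay blinded.

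The cost is protocol wording and a little reporting work by existing staff. Sample size, endpoints and the blinding of sites do not change. With no efficacy comparison made, the primary test's two-sided 0.05 is untouched.
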